***Participant Compensation:***

All participants will be compensated for their participation in this study and completion of all study visits is not required for receipt compensation. For Phase One, subjects will be paid \$10/hour, not to exceed \$70 for the baseline-screening visit. They will receive \$100 for the medication visit, and they will receive \$50 for the 24-hour follow-up visit. They will also be reimbursed for transportation based on mileage or receipts provided up to \$50 per visit. At the discretion of the investigator, subjects may be reimbursed for additional costs including travel, parking, transportation, meals, or other expenses. Subjects will be asked to provide receipts so that they can be reimbursed for these expenses, as applicable. For Phase Two, subjects will be paid \$10/hour, not to exceed \$70 for the baseline-screening visit. They will receive \$50 per visit for all remaining visits for a possible of 7 visits or \$350 (i.e., infusion 1, 24-hour follow-up, 7-day follow-up, 14-day follow-up/infusion 2, 24-hour follow-up, 7-day follow-up, 14-day follow-up) and will be reimbursed for transportation based on mileage or receipts provided up to \$50 per visit. Payments for this study are processed through Yale University. As such, participants' names, addresses and social security numbers will be provided to the Yale University Accounts Payable department in order to process subject payment for participating in this study. Participants may be asked to complete a W-9 form (federal request for taxpayer identification and certification), which allows Yale to process their payment and potentially report their earnings to the IRS. Payment may be made to participants in cash on the day of each visit, at the discretion of the PI. For any cash payments, participants will be asked to sign a receipt acknowledging payment and the amount they were given. Most participants will receive payments in the form of a check or through Yale University's debit card system. The debit cards will be offered through the YCCI OnCore ePayments system and will be our preferred payment option. Subjects will be informed that they will receive payment via a Bank of America pre-paid debit card. We will provide their name, address, and telephone number to the Bank of America for processing and their card will be related to their name and number. Their SSN or other information will not be provided. All compensation information will be discussed in the informed consent process. Yale will also send subjects an IRS 1099 form reporting the amount of money paid to them.

For Phase Three, subjects will be paid \$10/hour, not to exceed \$70 for the baseline-screening visit. They will receive \$50 per visit for all remaining visits for a possible of 6 visits or \$300 (i.e., infusion 1, 24-hour follow-up, 7-day follow-up, 14-day follow-up, 21-day follow-up, 28-day follow-up). At the principal investigator's discretion, further subject payment may be made for travel, parking, lodging, food, or transportation. Payment will be received through the mail in the form of a check from the VA, unless participants have arranged for direct deposit through the VA. Payment by check may take up to 6 weeks and is subject to withholding for outstanding debts; for

example, defaulted student loans, child support, or back taxes. If participants have any federal debt, there is a possibility that they will not receive any money after their participation.

There will be no charge to participants for any aspects of this study including services, testing, evaluation, or medications. However, some Veterans are required to pay a co-payment for medical and other services provided by the VA Connecticut Healthcare System that are not part of the study. These co-pay requirements will continue to apply to medical care and services provided by VA that are not part of this study.

***Data Analysis:***

This study, investigating the impact of sirolimus on ketamine's rapid antidepressant effects, is the first of its kind. In order to assess study utility and to determine if medication dose adjustments may be useful, we plan to do interim analyses after completion of the first 6 subjects, with subjects randomized according to block randomization (block of six). We propose to study 30 patients, overall. This sample size is feasible within the funding available for this project and will provide 80% power for detecting ketamine-sirolimus interaction effects of moderate size ( $d'=.53$ ), assuming a two-tailed alpha=.05. The data analysis plan is provided only for the primary outcome variable, the MADRS score. The normality of the data will be tested initially using probability plots and the Kolmogorov-Smirnov tests. These data are frequently skewed and so we plan to analyze them using a non-parametric approach to repeated measures data. The data will be first ranked and then fitted with a mixed-effects model with an unstructured variance-covariance matrix and p values adjusted for ANOVA-type statistics. In these models sirolimus (active vs. placebo) and time will be fitted as within subjects variables. All interactions will be fitted. Age and sex will be treated as covariates/grouping factors. Post-hoc analyses will be conducted to interpret interactive effects significant at the p=0.05 level. Subject will be used as the clustering variable. Plasma ketamine and ketamine metabolite levels will be analyzed using linear mixed models. All secondary measures will be assessed using similar methodology. Behavioral measures of Phase 3 will use similar methodology. The collection, processing and analysis of peripheral inflammatory biomarkers will be completed under a separate protocol and consent (i.e., CA0008).

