**Days 3-7/ Phone Follow-Up:**

After the Day 2 in-person follow-up, to further assess the safety of combined ketamine and sirolimus, a study clinician will contact Phase One participants by telephone, daily until Day 7. During these daily telephone follow-ups, subjects will be asked about potential side effects or interaction effects they may be experiencing related to the study medications.

After three participants undergo Phase One of this study, The PI will report findings and any issues to the Data and Safety Monitoring Committee (DSMC). The PI will not proceed to Phase Two of the study without a review and recommendation of continuation by the DSMC and subsequent full HSS review and approval of the DSMC's report.

Note: Participation in Phase One will not exclude subjects from participating in Phase Two if they so choose.

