***Privacy:***

All reports generated from the data obtained through this study will protect the confidentiality of the subjects who participate in this study. In case of a medical emergency, the medication group blinding can be broken by the principal investigator or a designated covering staff member, in order to supply information required for emergency medical care of research subjects. All subjects will be given a “wallet card” which identifies them as a study participant and lists the emergency contact numbers. If a subject shows clinical deterioration (worsening of depressive symptoms that is higher than 25% of baseline MADRS scores), the participant will exit the study and a study psychiatrist (or APRN) will determine whether a higher level of care (e.g. referral to treating psychiatrist or referral to emergency or inpatient care) is needed.

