### **Research Plan and Study Procedures:**

This is a double blind, placebo-controlled, crossover, randomized controlled trial investigating the impact of sirolimus on ketamine's antidepressant effects in participants with antidepressant-resistant depressive symptoms. Participants will be treated twice with ketamine 0.5 mg/kg infused over 40 minutes, combined with a single dose of sirolimus 6 mg orally or placebo. The 2 infusions of ketamine are separated by at least 2 weeks interval because based on previous studies the majority of patients return to their baseline depression severity within this time period. A description of each study visit is provided here and summarized in Figure 3. See Table 1 for detail regarding the schedule of study events.

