#### ***Day 1 / Infusion 1:***

First, the MADRS assessment will be completed to confirm that the participant continues to have significant depressive symptoms (i.e. MADRS  $\geq 18$ ) prior to proceeding with Infusion 1. Participants will be rescheduled if depression severity was not met‡. If depression severity is confirmed, Infusion 1 procedures will be completed as follows:

- Subjects will present to the VACHS to complete vitals and provide a urine sample for drug and pregnancy testing.
- Subjects will receive a single 6 mg oral dose of sirolimus or placebo, dependent on their randomization. They will be monitored for any acute allergic reaction or other adverse event. Clinical assessments will be administered throughout the infusion visit, including PSWQ, PSQI, MADRS, QIDS-SR, SAFTEE, CGI, HAM-A, CADSS, PANSS\*\* (assessment measures are described below).
- Intravenous lines will be placed.
- A blood draw for sirolimus level will occur prior to the beginning of the ketamine infusion.
- Ketamine 0.5 mg/kg will be infused over approximately 40 minutes. Subjects will be monitored closely by study physician and nurse.
- A blood draw for ketamine will occur during the ketamine infusion.
- One additional blood draw for sirolimus will occur shortly before the participants are discharged from their study visit.
- Subjects may be discharged home after being cleared by a study physician.

‡ Screening procedures will be repeated if participant was not randomized within 60 days of screening. \*Blood pressure, heart rate, and oxygen saturation will be recorded every 10 minutes during infusion (T0-40 minutes). \*\* Items that could not change within a session, e.g. sleep and appetite, will be carried forward from the initial ratings.

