**Moderate Risk DSMP**

***1. Personnel responsible for the safety review and its frequency:***

The principal investigator, [name]., will be responsible for monitoring the data, assuring protocol compliance, and conducting the safety reviews at the specified frequency, which must be conducted at a minimum of every 6 months (including when reapproval of the protocol is sought). During the review process, the principal investigator (monitor) will evaluate whether the study should continue unchanged, require modification/amendment, continue or close to enrollment. Furthermore, a data and safety monitoring committee (DSMC) of independent researchers/clinicians (including an ethicist and statistician) will review adverse events. The DSMC committee will review the study prior to the initiation of Phase One subject enrollment. The DSMC will be consulted again prior to Phase Two of the study, at which point the committee members will determine whether this study can be safely conducted on an outpatient basis. In addition, the DSMC will conduct a safety assessment twice yearly. Either the principal investigator, the DSMB (Phase 1 & 2), or the VA IRB have the authority to stop or suspend the study or require modifications.

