***2. The risks associated with the current study are deemed moderate for the following reasons:***

1. We do not view the risks associated with ketamine infusion and sirolimus dosing as minimal.
2. Given the established safety and validity of the use of ketamine and sirolimus, we do not view the proposed study as high risk.

Although we have assessed the proposed study as one of moderate risk, the potential exists for anticipated and/or unanticipated adverse events, serious or otherwise, to occur since it is not possible to predict with certainty the absolute risk in any given individual or in advance of first-hand experience with the proposed study methods. In order to assess safety in this patient group, we will conduct an interim data analysis after the first 5 subjects are completed.

Therefore, we provide a plan for monitoring the data and safety of the proposed study as follows:

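### Do the unreconciled interim looks, after 6 subjects in one section and after 5 in another, undermine the blinded Phase Two comparison?

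*Combined protocol and SAP*

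**What the plan says.** Two places in the combined protocol and SAP plan an early look at the data.

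- **Data Analysis.** The relevant words are "to determine if medication dose adjustments may be useful, we plan to do interim analyses after completion of the first 6 subjects". The same sentence gives study utility as a further purpose and adds that subjects are randomized in blocks of six. The section then sets 30 patients, 80% power at d' = 0.53, and a two-tailed alpha of 0.05.
- **Moderate Risk DSMP, item 2.** "In order to assess safety in this patient group, we will conduct an interim data analysis after the first 5 subjects are completed".

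Phase One has its own checkpoint: "After three participants undergo Phase One of this study, The PI will report findings" to the monitoring committee, and Phase Two waits for that review.

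On access to treatment codes, the Privacy paragraph says: "In case of a medical emergency, the medication group blinding can be broken by the principal investigator or a designated covering staff member". Item 1 of the DSMP says the principal investigator "will be responsible for monitoring the data, assuring protocol compliance, and conducting the safety reviews at the specified frequency". It also has an independent committee, including an ethicist and a statistician, review adverse events and assess safety twice a year. Authority to act rests with the principal investigator, "the DSMB (Phase 1 & 2), or the VA IRB have the authority to stop or suspend the study or require modifications".

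On treatment, Research Plan and Study Procedures describes ketamine "combined with a single dose of sirolimus 6 mg orally or placebo". On each infusion day, "A blood draw for sirolimus level will occur prior to the beginning of the ketamine infusion".

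**The concern.** The counts differ, the sections do not cross-refer, and item 2 of the DSMP does not name a phase. A reader cannot tell whether this is one look with two counts or two looks.

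Three things could be at stake in a double-blind crossover with a clinician-rated outcome.

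1. **The blind.** Judging utility or dose is easier with data split by session, and no section says who may see such data. Measured sirolimus levels would show anyone who saw them which session was active. If that reached a MADRS rater, the comparison could be biased.
2. **The regimen.** A look meant to inform dose could lead to participants being treated under different regimens.
3. **The final test.** If an early look tested efficacy at 0.05 and could end the trial with a positive claim, the overall error rate would exceed 0.05.

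The Background section already reports Phase Two results, including a treatment-by-time p of 0.04 in the figure legend, and mentions neither look.

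**Working it through.** **1. Do 5 and 6 conflict?** Set side by side:

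- Data Analysis: after 6 subjects; study utility and dose; tied to a block of six.
- DSMP item 2: after 5 subjects; safety.

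The purposes differ, and the 6 has its own rationale as one complete block. Two looks, each with its own purpose, is a coherent reading. Counting the 3 Phase One subjects within the 5 is possible, but nothing in the text suggests it, and Phase One has its own report and approval step.

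**2. The plan's own power figure.** Inputs from Data Analysis: n = 30, d' = 0.53, two-tailed alpha 0.05. A paired t-test stands in here for the ranked mixed model.

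- Noncentrality = d' × √n = 0.53 × √30 = 2.90, with 30 − 1 = 29 degrees of freedom.
- Power from the noncentral t distribution = 0.801.
- The smallest n that reaches 80% is 30.

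The stated 80% is therefore a single final paired test, with no alpha set aside for interim looks. That is right if the looks do not test efficacy.

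**3. What an efficacy test at the looks would have cost.** This case is hypothetical. Assume each look applies an unadjusted two-sided 0.05 test of the primary contrast and a significant result ends the trial as positive. The correlation between interim and final statistics is √(m/30). The overall type I error is 1 − P(all |Z| < 1.96).

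- Look at 6: correlation √(6/30) = 0.447; error 9.2%.
- Look at 5: correlation √(5/30) = 0.408; error 9.3%.
- Both looks: error 11.0%.

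The plan gives neither look an endpoint, test, boundary or rule for stopping early with success. Without those, the figures do not apply and the final error stays at 5%. Stopping for lack of promise would not raise it.

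**4. Could looks this small serve as efficacy analyses?** With the same paired t-test at d' = 0.53, power is about 19% with 6 subjects and about 15% with 5. That fits early feasibility and safety checks better than tests of the primary hypothesis.

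**5. Was there one regimen?** Research Plan and Study Procedures, Ketamine Administration, and Sirolimus or Placebo Dosing all state the same one. Phase Three Research Procedures describes its treatment as identical to Phase Two apart from having a single treatment day. These are plan statements rather than a record of conduct, but they all point to no change.

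**6. What would rewording change now?** Phase Two results are already reported. Phase Three is open-label with one treatment day, so it has no blind to protect and no randomized contrast to test.

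**The case for a change.** The strongest case is that a blinded comparison rests on knowing who saw what. No section assigns either look to the independent committee or says whether data are pooled or split by treatment. Because utility and dose are hard to judge from pooled data, and the look sits in the section that plans the MADRS analysis, asking about by-arm access is reasonable. The count can matter too. In a balanced block of six, by-arm data on five members would reveal the sixth member's sequence, if the first completers came from one block. And had the regimen changed after six subjects, setting them aside would leave 30 − 6 = 24 and 70% power at d' = 0.53.

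The silence on access stands as a gap in the wording. The rest depends on events the documents do not describe. No section says that either look is by arm, names sirolimus levels as an interim variable, or gives a MADRS rater interim access. An independent committee with a statistician is in place for Phases One and Two, and it is a natural home for such looks, although the text does not assign them. The 70% figure needs a regimen change that the text points against. It also discards participants who each served as their own control and would still supply a within-subject contrast. The Background paragraph and figure legend summarise a fuller report that is not available here, so their silence does not show that the record is missing.

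**Conclusion.** The concern does not call for a change. The two sentences leave open whether there is one look or two, and who sees the data. That is an ambiguity in drafting, not a demonstrated contradiction or a flaw in the analysis.

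On the plan as written, the effect on inference is nil. The final two-tailed 0.05 test is unaffected, and the 80% power reproduces as 80.1%. This rests on three assumptions: neither look tested efficacy with the option of an early positive claim, MADRS raters stayed blind, and one regimen was used throughout Phase Two. The documents contradict none of these, and on the regimen they offer positive support.

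Analysts would sensibly treat the look after 5 as a safety review and the look after 6 as a check at the end of the first block. Rewriting the sentences now could not alter the Phase Two data and has no bearing on the open-label Phase Three.

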***Sirolimus or Placebo Dosing:***

Subjects will receive a single 6 mg oral dose via oral solution of sirolimus or a dose of placebo approximately two hours prior to the infusions. As above, the order of placebo and sirolimus is randomized. The sirolimus dose as well as the placebo solution will be given in 2 ounces of orange juice, followed by 4 oz of water. As for the tolerability of single dose of sirolimus, based on data in healthy subjects and consultation with [name], Director of Transplant Medicine, Yale University, an expert with sirolimus treatment, it is expected that a single 6 mg oral dose will produce minimal adverse effects.

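### Does the interim look after six completers, with dose adjustment in view, need a rule now for how those already treated would be analysed?

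*Combined protocol and SAP*

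**What the plan says.** The Data Analysis section gives the interim look two purposes, study utility and dosing: "to determine if medication dose adjustments may be useful, we plan to do interim analyses after completion of the first 6 subjects". Randomisation is in blocks of six. The text then sets a total of 30 patients for the whole study and says this "will provide 80% power for detecting ketamine-sirolimus interaction effects of moderate size" (d' = 0.53, two-sided 0.05). One primary model follows: "In these models sirolimus (active vs. placebo) and time will be fitted as within subjects variables", with age and sex as covariates. It has no term for regimen or for stage of the trial.

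Changes to the study are covered in item 1 of the Moderate Risk DSMP. The principal investigator "will evaluate whether the study should continue unchanged, require modification/amendment, continue or close to enrollment", and the investigator, the DSMB or the VA IRB "have the authority to stop or suspend the study or require modifications". Item 2 adds a safety look: "In order to assess safety in this patient group, we will conduct an interim data analysis after the first 5 subjects are completed".

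The dosing sections give a single regimen. Research Plan and Study Procedures: "Participants will be treated twice with ketamine 0.5 mg/kg infused over 40 minutes". Sirolimus or Placebo Dosing: "Subjects will receive a single 6 mg oral dose via oral solution of sirolimus or a dose of placebo". Ketamine Administration agrees with both.

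**The concern.** A look that may lead to a different dose raises the question of what happens to people treated on the old one. They could be pooled with the rest, analysed separately, or replaced. The plan picks none of these and does not say that power would be restated.

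Two things would be at stake. If everyone were pooled, the active-versus-placebo contrast would average two regimens. If the set were chosen after outcomes were seen, the 5% error rate would no longer be protected.

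The plan also does not say whether efficacy could be claimed at the look, or whether the looks after five and after six completers are the same one.

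**Working it through.** **Inputs from the Data Analysis section:** 30 completers, d' = 0.53, two-sided alpha 0.05, first look after 6 completers. From the Phase Two Subjects section: 45 randomised to retain 30 completers.

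**Method.** Paired t-test: noncentrality = d × √n, df = n − 1, power from the noncentral t. This approximates the planned rank-based mixed model; a signed-rank simulation gives values about 2 points lower.

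**Plan as written.** 0.53 × √30 = 2.903, critical t (29 df) = 2.045, power 80.1%. The stated 80% reproduces.

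**If a dose changed and six participants were left out**
- Not replaced: n = 24, 0.53 × √24 = 2.596, critical t (23 df) = 2.069, power 70.1%.
- Replaced: 30 pairs on the final regimen, power 80.1%. This needs 36 completers, or 36 × 45/30 = 54 randomised.

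**If the later effect differs.** The ratios 0.75 and 1.25 are assumptions; the documents give none. Pooled figures are simulated with 6 early pairs at d = 0.53 and 24 later pairs.

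| Later d | 30 pairs, all at later d | 24 pairs | Pooled 6 + 24 |
|---|---|---|---|
| 0.3975 | 55.8% | 46.3% | 61% |
| 0.53 | 80.1% | 70.1% | 80% |
| 0.6625 | 93.9% | 87.4% | 92% |

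Within a row, dropping six costs 9.5, 10.0 and 6.5 points. The rest of the fall from 80% to 46% comes from assuming a weaker drug effect, which no analysis rule would alter. In the top row pooling gives more power than 30 pairs all at the later effect, so 61% cannot be charged to the missing rule either.

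**Number treated before a change.** The look is triggered by completion, which comes at Day 29 at the earliest, and the documents do not say that recruitment pauses. More than six could therefore have been treated. Unreplaced exclusion of 6, 8, 10 or 12 leaves 24, 22, 20 or 18 pairs, with power 70%, 66%, 61% or 56% at d = 0.53.

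**Type I error (simulated, 400,000 trials)**
- All 30, fixed in advance: 5.0%. Last 24, fixed in advance: 5.0%.
- Success declared if either set gives p < 0.05: about 7.1%.
- Efficacy tested at 0.05 after 6 and again after 30: about 9.3%.

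The last two need a practice that the plan does not describe. It offers no choice of set and no efficacy stopping; the purposes given for the looks are utility, dosing and safety.

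**The case for a change.** The strongest case for acting is that dose adjustment is a named purpose of the look, so its consequence for the primary analysis should be written before outcomes are seen. Nothing obliges a later amendment to cover the analysis set, and it would be drafted after six people's results were known. The Phase 2 treatment-by-time interaction is reported at p = 0.04 in the figure legend under Significance. With a result that close to 0.05, a reader would want to know that one regimen and one pre-set population lie behind it. The remedy would cost a few sentences.

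Much of this stands as description. No section closes the gap, and the arithmetic is right. The allowance of 45 randomised for 30 completers covers dropout and discontinuation, not a superseded regimen.

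It does not carry through to a change. Phase 2 has been run and reported, so a rule added now cannot govern its conduct. Phase 3 is a single open-label arm with no sirolimus-placebo contrast for the rule to protect. The current text, written after the Phase 2 results, still gives one regimen, and describes Phase 3 treatment as the same as Phase 2 except for the single open-label treatment day. Whether the look took place is something the Phase 2 report can state; it is not a defect in the analysis plan.

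**Conclusion.** No change to the plan is needed. The missing text is a rule for an event that the plan only contemplates and that would require an amendment. The single total of 30 and the single model supply a workable default of including everyone. Under that default, a test of no sirolimus effect on either regimen stays valid at 5%, and the estimate is a weighted average of the two. An analyst facing an actual change would name the set and restate power in the amendment.

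On the plan as written, power is 80.1% and type I error 5%. If a change occurred, the loss from excluding six without replacement would be about 10 points at an unchanged effect (80% to 70%), and more if others were already under treatment. These figures rest on the paired t approximation and on d' = 0.53 being the standardised within-person difference. Nothing in the documents shows that a dose was changed.

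The looks after five and after six completers differ in stated purpose. Whether they are one look or two is a small point of clarity that does not affect the final test, since neither is described as a test of efficacy.
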